6.3.1.2 Reference treatment

As the reference treatment, a commercially available medication, your batch number and IPP will be kept as proof of the characterization of said product.

- **Sophixín Ofteno®**
 -
 - Active substance: Ciprofloxacin 0.3%
 - Pharmaceutical form: Ophthalmic solution
 - Prepared by: Sophia Laboratories, S.A. of C.V
 - Dosage: 1 drop in both eyes, 8 times a day during the waking period
 - Description of the solution: transparent solution, free of visible particles.
 - Description of container: sterile multi-dose bottle

Table 5. Sophixin Ofteno quali-quantitative formulation

Type of agent	Amount mg/mL	Function
Ciprofloxacin ⁽¹⁾	3.0	Active principle
Boric acid	Without showing	additive
Benzalkonium Chloride ⁽²⁾	0.22	additive
Sodium chloride	Without showing	additive
Disodium edetate dihydrate	Without showing	additive
Water for injection preparation c.b.p. ⁽³⁾	1.0 ml	vehicle

Quali-quantitative formulation of Sophixin Ofteno®. The concentration of the active ingredients is shown, as well as the substances that act as an additive.

OBSERVATIONS:

(1) It is added as Ciprofloxacin Monohydrate.

(2) 50% solution.

(3) How much is enough for.

(4) 4N sodium hydroxide solution.

(5) c.b.p. (how much is enough for).

6.3.2 Strategies to improve adherence and procedure to monitor adherence

1. 1. Direct questioning by the PI about the application of the intervention.
2. 2. Depending on the IP, messages can be sent or reminder calls can be made.
3. 3. Delivery of a printed chronogram specifying the date of the visit and its activities
4. 4. Review on each visit of the subject's diary.

6.3.2.1 Procedure to monitor adherence

Adherence monitoring will be done in the research center through the diary of the subject, will be done as follows:

$$Ad = (A_r)100/A_i$$

Ad = Adherencie

A_r = Registered applications

A_i = Applications indicated for the intervention

This result will allow the PI to determine if the subject continues in the study according to the stipulations of the elimination criteria.

6.3.2.2 Procedure to determine adherence

The final adhesion will be determined by the sponsor by means of the weight of the bottle.

Before delivering the medication to the research center, the weighing of the bottles to be delivered must be carried out. After the return of the medication by the center will be weighing. The weighing will be carried out according to the procedures regulated by the sponsor.

The adhesion will be calculated considering: the weight of the empty bottle, the weight of the drop, the weight of the bottle with the content, the calculation of the total of drops to be applied during the entire time of intervention and the total weight of the drops applied. The following simplified formula will be used:

$$Ad = \frac{(P_i - P_f)100}{P_T}$$

Where:

Ad = adhesion

P_i = weight of the bottle delivered to the subject at the start

P_f = weight of the bottle returned by the subject

P_T = weight of the posology indicated for the intervention.

$$P_T = (P_g)G$$

Where:

P_g = weight of the drop of the intervention, determined by the department of research and development

G = number of drops indicated for the intervention.

6.3.3 Treatments and concomitant interventions allowed and prohibited during the study

The use of concomitant medications by any route of administration during the intervention period will not be allowed. Except those specified for the study procedures. The objective of this restriction is to avoid pharmacological interactions that could alter the results of the evaluated variables.

6.3.4 Treatment management

The interventions will be provided by Sophia Laboratories, S.A. of C.V, for each research center. They will be labeled, reconciled and weighed previously. The handling of the treatment will be under the responsibility of the researcher or a designated member of his team.

6.3.4.1 Delivery and reception

The delivery will be made in closed cardboard boxes by means of a courier service or directly by the sponsor's staff to the address of the research center according to the study plan.

The reception will be exclusively carried out by the research center team, including the researcher. You must check the good condition of the primary packaging (box). In the event that it shows alterations or defects in its integrity that from its judgment could have damaged the content, it should report it to the sponsor. If the package does not show significant defects, it will proceed to open it.

Inside you must locate the acknowledgment document and the logger (data logger) of temperature and humidity. You should check that the registered temperature and humidity comply with the specifications for transport and shelter (see section 6.3.4.2 Storage). Verify the content (interventions) with what is reported in the document. In case the document corresponds to the content, it will sign the receipt and send it to the sponsor. Otherwise, notify the sponsor.

In the study center, the personnel assigned by the IP will deliver to the inpatients the corresponding treatment, sufficient to complete the indicated applications. The center must register the medicine delivered.

6.3.4.2 Storage

The medication must be stored in a secure area with restricted access.

It should be stored at room temperature at <30° Celsius.

The research center has the obligation to record, in the format designated by the sponsor, the temperature and humidity registered in the data logger. This record should include the current temperature and humidity, as well as the minimum and maximum of each of these. It must be done at least once a day, on business days.

Said data will be compared by the clinical monitor according to the registration in the data logger.

6.3.4.3 Return

The research subjects will return to the personnel indicated by the IP in the center their treatments in the final visit. The refund will be made by the research center when the sponsor indicates it. Prior to the return the research center must make a count of the assigned medication and the remaining medication, with the aim of creating an inventory which serves for the final filling of the medication return form.

6.3.5 Overdose

Overdosage with PRO-174 or Sophixin Ofteno® is not likely to cause effects that threaten function, the organ or less, life. The above, because increasing the number of drops instilled in an application will not increase the exposure to the drug, since the lacrimal lake does not have the capacity to contain a volume greater than one drop, spilling the rest. In case of increasing the frequency of instillations, an increase in the incidence of adverse reactions could be seen (eg, foreign body sensation, headache, photophobia, etc).

For purposes of this protocol we understand as overdosage the increase in 25% of the indicated instillations. That is, 10 or more applications per day on days 1 and 2, or 5 or more applications on days 3 to 7.

1. The report of the overdose will be made in the following tenor:
2. How a deviation to the protocol. The regime instructed in the protocol was not followed.
3. How an EA. Only if it is associated with signs and symptoms.
4. How an EAS. If you meet the criteria to be classified as an EAS.

6.4 Outcome variables

6.4.1 Security variables

6.4.1.1 Primary outcome variables

- Presence of adverse events.
- Intraocular pressure.
- Visual ability
- Laboratory tests: BHc, QS and PFH.
- Ocular surface staining with fluorescein and lissamine green using the Oxford scale.
- Ophthalmological signs: conjunctival hyperemia, chemosis.

6.4.1.2 Primary outcome variables of tolerability Ardor

- Foreign body sensation
- Itching
- Eye comfort index.

6.4.1.3 Secondary outcome variables

- Rupture time of the tear film
- Life signs: FC, FR, TAS.
- Posterior segment

6.4.2 Efficacy variables.

6.4.2.1 Primary outcome variables

It does not apply because it is a phase I study.

6.4.2.2 Secondary outcome variables

It does not apply because it is a phase I study.

6.4.3 Methods and scales to be used for the measurement of the variables

Variable	Unity	Symbol	Type	Measuring method	Normal value
Age	Years	--	Continuous	Calculation from the date of birth	NA
Gender	Female/ Male	F / M	Nominal	Direct questioning	NA
Adverse events	Number of cases	n	Discreet	Count	NA
Intraocular pressure	Milimeters of mercury	mmHg	Continuous	Goldman's applanation tonometry	11 - 21
Visual ability	Fraction	Snellen	Nominal	Primer	
Tear rupture time	Seconds	s	Continuous	Direct count	> 10
Eye comfort index	points	--	Discreet	Questionnaire	
	Present / Absent	--	Nominal	Comprehensive valuation	Absent
Vital signs					
Heart rate	Beats per minute	lpm	Discreet	Auscultation	60 – 100
Breathing frequency	Breaths per minute	rpm	Discreet	Auscultation	12 – 24
Systemic blood pressure	Milimeters of mercury	mmHg	Continuous	Non-invasive auscultatory measurement	< 120 / 80
Previous segment					
Ocular surface staining	Degrees	--	Discreet	Direct observation with fluorescein and green lysamin stain	Oxford Scale
Ophthalmologic signs and symptoms					

Variable	Unity	Symbol	Type	Measuring method	Normal value
Conjunctival hyperemia	Normal / Very Light / Mild / Moderate / Severe	--	Ordinal	Direct observation. Classification of Efron.	Normal
Chemosis	Present / Away	--	Nominal	Direct observation	Absent
Burning	Severity: Absent, very mild, mild, moderate and severe	--	Nominal	Direct questioning	Absent
Foreign body sensation	Severity: Absent, very mild, mild, moderate and severe	--	Nominal	Direct questioning	Absent
Pruritus	Frequency: At all times, almost at all times, 50% of the time, almost in no time, at any time	--	Nominal	Direct questioning	Absent
Posterior segment					
Macula	Normal / Abnormal	--	Nominal	Direct observation	Normal
Optical disk integrity	Normal / Abnormal	--	Nominal	Direct observation	Normal
Blood count					
Erythrocytes		M/uL	Continuous		
Hemoglobin	Grams over deciliter	g/dL	Continuous		
Hematocrit	Percentage	%	Continuous		
VGM	Femto liters	fL	Continuous		

Variable	Unity	Symbol	Type	Measuring method	Normal value
HCM	picograms	pg	Continuous		
CMHbG	Grams over deciliter	g/dL	Continuous		
Leukocytes	Thousands per liter units	Mil/uL	Continuous		
Platelets	Thousands per liter units	Mil/uL	Continuous		
Myelocytes	Percentage	%	Discreet		
Metamyelocytes	Percentage	%	Discreet		
Bands	Percentage	%	Discreet		
Segmented	Percentage	%	Discreet		
Lymphocytes	Percentage	%	Discreet		
Monocytes	Percentage	%	Discreet		
Eosinophils	Percentage	%	Discreet		
Basophils	Percentage	%	Discreet		
Blastos	Percentage	%	Discreet		
Blood chemistry					
Glucose	Milligrams on deciliter	mg/dL	Continuous		
Urea	Milligrams on deciliter	mg/dL	Continuous		
Creatinine	Milligrams on deciliter	mg/dL	Continuous		
Liver function tests					
Alanine transferase	Units on liter	U/L	Continuous		
Aspartate transferase	Units on liter	U/L	Continuous		
Total bilirubin	Milligrams on deciliter	mg/dL	Continuous		
Direct bilirubin	Milligrams on deciliter	mg/dL	Continuous		
Indirect Bilirubin	Milligrams on deciliter	mg/dL	Continuous		

Table 6. Scales to be used

The following describes the methods and scales that will be used for the measurement of the variables, which are in strict alphabetical order:

6.4.3.1 Visual ability

Visual acuity (VA) is a test of visual function. Spatial visual acuity is the ability to distinguish separate elements of an object and identify them as a whole. It is quantified as the minimum separation angle (located at the nodal point of the eye) between two objects that allows perceiving them as separate objects.

Snellen's notation is described as the distance at which the test is performed, divided by the distance at which the letter is vertically equivalent to 5 arc minutes. Thus, at 6 meters a letter 6/6 (20/20) equals 5 minutes of arc, a letter 6/12 (20/40) equals 10 minutes, and a letter 6/60 (20/200) equals 50 minutes. The Snellen fraction can also be expressed as a decimal (ie $20/20 = 1$ and $20/40 = 0.5$). [26]

The VA will be evaluated basally, without refractive correction with the Snellen chart. Which will be located in a place with adequate lighting, natural or artificial and at a distance of 3m from the subject to be evaluated. The visual acuity of each eye will be taken, starting with a right eye (DO) asking the subject to keep both eyes open and using an occluder to cover the left eye (OS); the subject will read aloud the lines that the evaluator points out, the line of smaller letters that he reaches to see will be annotated by the fractional evaluator as the DO of the DO in the clinical record. Proceed to the OS with the same method.

Subsequently the best refractive correction of the subject will be made and the examination will be repeated using the obtained refraction. This result will be reported as CV, it will be written in fraction in the clinical file and in the CRF, in addition in the CRF it will be written in decimal. By definition, the CV can not be inferior to the AV.

6.4.3.2 Eye comfort index

It is a questionnaire designed to measure the irritation of the ocular surface with Rasch analysis to produce estimates on a linear scale of intervals (ratings: 0-100). Similar to the index for ocular surface diseases, the ocular comfort index (ICO) evaluates symptoms. The ICO contains 8 items (one positive and eight negative) that focus on the discomfort associated with alterations of the ocular surface. Each of these questions has two parts, which inquire separately the frequency and severity of the symptoms. [27] See annex 13.1 Index of ocular comfort

The evaluator will deliver the questionnaire to the subject and allow the subject to answer it calmly without any pressure and / or coercion, will only assist him if he has difficulty understanding any of the questions.

6.4.3.3 Eye surface integrity:

This will be done by means of biomicroscopy using the slit lamp of the research center. A full assessment of the previous segment will be made, which will be recorded in the clinical file. The lighting techniques used will be at the discretion of the IP.

The variables that will be registered in the CRF in this protocol, and correspond with the variables, are:

- *Conjunctival hyperemia.*

It is defined as the simplest reaction of the conjunctiva to a stimulus, a red appearance secondary to the vasodilation of the conjunctival vessels of variable intensity. He will graduate using the Efron scale. [28] See annex 13.2 Efron scale for conjunctival hyperemia

- *Chemosis.*

It is defined as conjunctival edema, the result of an inflammatory reaction. It is qualified as present or absent. The evaluator will use a narrow beam of light at 60 ° and will measure if

the conjunctiva separates from the sclera at $\geq 1/3$ of the total palpebral opening or if it exceeds the gray line. [29]

6.4.3.3.1 Stains

- *Staining with green lysine.*

A drop of topical anesthetic will be instilled in the conjunctival cul-de-sac, then a second drop will be applied to the tip of the strip of green lysine and it will be allowed to slip towards the bottom of the sac. It is essential to quickly evaluate the staining, in sequence, first in the DO and then the OS, so that the observed patterns are equally bright. [30] See Annex 13.3 Oxford Scale

- *Fluorescein staining.*

A drop of topical anesthetic will be instilled into the conjunctival cul-de-sac, then a second drop will be applied to the tip of the fluorescein strip and it will be allowed to slip to the bottom of the sac. It is essential to quickly evaluate the staining, in sequence, first in the DO and then the OS, so that the observed patterns are equally bright. This valuation will be made with the cobalt blue filter. [30] See Annex 13.3 Oxford Scale

For both stains, the value obtained according to the Oxford scale will be registered in the CRF.

6.4.3.4 Presence of adverse events

The management of the EAs will be done according to what is described in section 9.3 Adverse events

The PI will register in the corresponding section of the CRF the EAs that come to present the subjects of the study in addition to referring it in its essential document.

6.4.3.5 Intraocular pressure

Tonometry is the objective measure of IOP, based primarily on the force required to flatten the cornea or the degree of corneal indentation produced by a fixed force. Goldman's tonometry is based on the Imbert-Fick principle. [26] Tonometry will be performed, after instillation of a drop of topical anesthetic (tetracaine 0.5%), with fluorescein and the use of cobalt blue filter (after evaluation of corneal surface staining). There will be 3 shots, which will be recorded in the clinical file and the average will be registered in the CRF.

6.4.3.6 posterior segment

The evaluation of the posterior segment will be carried out under medication mydriasis (tropicamide 0.8% / phenylephrine 5%), in the slit lamp with an aerial loupe (at the choice of the PI). An integral assessment of the fundus (including optic disk, posterior pole and periphery) will be performed in search of abnormalities that alter the study result. Prior to mydriasis medicamentosa, the evaluation of the iridocorneal angle should be counted, in order to rule out an occludable angle, which is defined as a posterior trabecular mesh visible in less than 90 ° of the angular circumference. [31] [32] The result of the assessment will be recorded in the clinical file. The CRF will record the assessment of the macula and optic nerve as normal, abnormal or abnormality that does not affect.

6.4.3.7 Vital signs

The vital signs to be evaluated (FC, FR and TAS) can be measured by an assistant duly indicated in the organization of the center and the delegation of responsibilities, the technique to be used for the FC and FR will be with the count of repetitions in one minute by direct auscultation with stethoscope.

The SBP should be measured with 5 minutes of previous rest, in the left arm. The instrument can be manual or automatic according to the IP. It is necessary that all measurements are equal in circumstances. 3 measurements will be made, with a minimum interval of 5 minutes between them. The IP will record the average in the note and the CRF.

6.4.3.8 Ocular symptomatology

The subject will be questioned directly about the presence in general (since the last visit) of the following symptoms: burning, foreign body sensation and pruritus. Respond about the severity and frequency of symptoms such as:

Severity: Absent (0), very mild (1), mild (2), moderate (3) and severe (4)

Frequency: At all times (4), almost at all times (3), 50% of the time (2), almost at no time (1), at any time (0).

The number corresponding to each symptom will be registered in the CRF.

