6.2.3 Elimination criteria

- Withdrawal of the consent letter under information.
- Presentation of a serious adverse event.
- No tolerability or hypersensitivity to any of the compounds used during the tests (fluorescein, green lysine, tetracaine)
- No tolerability or hypersensitivity to any of the investigational drugs.
- Adherence <50% determined by the diary of the subject, of the established dose of the pharmacological intervention in any of the visits.

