6.5.1 Procedures to be performed per visit

6.5.1.1 Scrutiny visit

- **Signature of informed consent:** refers to the signing of the written informed consent document. See 10.3 Consent.

- General and ophthalmological clinical history: refers to the technical, clinical and legal document in which the patient's health conditions, medical acts and other procedures performed on the patient are recorded chronologically. It includes the anamnesis and comprehensive ophthalmological exploration that allows to discern the patient's eligibility. If the patient is taken from the established consultation of the study center, he / she will be able to use the existing clinical history, only having to perform an update.
- Taking laboratory samples: see 6.4.3.11 Laboratory tests.
- Pregnancy test: see 6.4.3.11 6.4.3.10 Pregnancy test.
- Eligibility criteria: refers to the review by the IP, where it states that the subject can be included in the study by meeting the inclusion criteria and not meeting the exclusion criteria. See 6.2 Eligibility criteria
- Intraocular pressure: see 6.4.3.5 Intraocular pressure
- Visual ability: see 6.4.3.1 Visual capacity
- TRL: see 6.4.3.9 Rupture time of the tear film
- Integrity of ocular surface: see 6.4.3.3 Integrity of ocular surface:
- Eye symptoms: 6.4.3.8 Ocular symptomatology
- Subsequent segment: see 6.4.3.6 Subsequent segment
- Vital signs: see 6.4.3.7 Vital signs
- Adverse events: see 6.4.3.4 Presence of adverse events6.5.1.2 Visita basal
- Review of laboratory tests: refers to the review and analysis by the IP of the results of the BH, QS and PFH. See 6.4.3.11 Laboratory tests.
- Eligibility criteria: with the laboratory results, the subject's profile will be finalized for inclusion or not.
- Assignment: It refers to determining the intervention that the patient will follow during the study. It will be done according to section 7. Methods. Assignment of the intervention. This assignment will be made at the baseline visit (day 0) and will go along with the indication to start the treatment period the next day (day 1).
- Delivery of intervention: Refers to the delivery of the product under investigation to the patient of the study, by the research center. It will be done according to sections 6.3.1 Managed treatments and 6.3.4.1 Delivery and reception.

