- Evaluation of variables: The data of the evaluation of the variables listed below can be taken from the scrutiny visit, as long as it does not exceed 7 days prior to this visit. It is the IP's prerogative to decide whether to use the information from the screening visit or to repeat the evaluations on this visit.
 - Intraocular pressure
 - Visual capacity
 - TRL
 - Integrity of ocular surface
 - Eye symptoms
 - Subsequent segment
 - vital sign
- Eye comfort index: see 6.4.3.2 Eye comfort index
- Delivery of the subject's diary: It refers to the delivery by the IP to the subject, the subject's daily instrument.
- Adverse events: see 6.4.3.4 Presence of adverse events

6.5.1.3 *Visita 1*

- Evaluation of adherence: refers to the assessment made by the IP according to section 6.3.2.1 Procedure to monitor adherence
- Adverse events: see 6.4.3.4 Presence of adverse events
- Intraocular pressure: see 6.4.3.5 Intraocular pressure
- Visual ability: see 6.4.3.1 Visual capacity
- TRL: see 6.4.3.9 Rupture time of the tear film
- Integrity of ocular surface: see 6.4.3.3 Integrity of ocular surface:
- Eye symptoms: 6.4.3.8 Ocular symptomatology
- Vital signs: see 6.4.3.7 Vital signs
- Submission of the subject's diary: see 6.5.1.2 Baseline visit
- Return / daily evaluation of the subject: refers to the delivery of the subject's diary to the IP by the subject. The PI will review the diary to assess its correct filler, evaluate postinstillation symptoms and record applications.
- Continuity assessment of the subject: refers to the determination by the IP and desire of the subject to continue with their participation in the study.

6.5.1.4 *Final Visit*

- Laboratory sample taking: ver6.4.3.11 Laboratory tests
- Pregnancy test: see 6.4.3.10 Pregnancy test
- Return of intervention: see 6.5.1.3 Visit 1.
- Evaluation of adherence: refers to the assessment made by the IP according to section 6.3.2.1 Procedure to monitor adherence
- Adverse events: see 6.4.3.4 Presence of adverse events
- Intraocular pressure: see 6.4.3.5 Intraocular pressure
- Visual ability: see 6.4.3.1 Visual capacity
- TRL: see 6.4.3.9 Rupture time of the tear film
- Integrity of ocular surface: see 6.4.3.3 Integrity of ocular surface:
- Eye symptoms: 6.4.3.8 Ocular symptomatology
- Subsequent segment: see 6.4.3.6 Subsequent segment
- Vital signs: see 6.4.3.7 Vital signs
- Eye comfort index: see 6.4.3.2 Eye comfort index
- Return / daily evaluation of the subject: see 6.5.1.3 Visit 1.

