8.3 Statistical methodology

8.3.1 Analysis of primary and secondary outcome variables.

The statistical analysis will be carried out by personnel from Sophia Laboratories, S.A. of C.V The statistical program SPSS version 19 (IBM Corporation, Armonk, NY, USA) will be used.

The designated personnel will be blinded to the intervention groups. The coding will be done using consecutive numbers for each intervention group.

The data will be collected and sorted in an excel sheet. Later they will be exported to the platform of the SPSS program. The variables will be categorized according to their nature.

The result of the continuous quantitative variables will be presented in measures of central tendency: media, standard deviation and ranges. **See Table 6.** Scales to be used

The normal distribution of the results will be obtained by the Kolmogorov-Smirnov test.

The statistical analysis of the continuous **quantitative variables** to find significant differences (p) will be the following:

- Intra-group analysis: Wilcoxon rank test.
- Inter-group analysis: Mann-Whitney U test.

The level of difference to consider significance will be of an alpha of 0.05 or less.

The result of nominal and ordinal qualitative variables will be presented in frequencies, proportions and percentages. See table 1 (section 6.4.3).

The statistical analysis to identify significant differences of the **qualitative variables** will be done by creating 2x2 contingency tables and will be done as follows:

- Intra-group difference: McNemar test.
- Difference between groups: test χ^2 (Chi-square) of Pearson.

The level of difference to consider significance will be of an alpha of 0.05 or less.

For the reporting of adverse events all eyes of those participants who were randomly assigned to an intervention group after the baseline visit will be considered. The results will be expressed in number of cases (eyes).

The final report of the results will be shown in tables or graphs, as appropriate.

It will be considered that the investigational drug is safe and tolerable when there are no clinical and statistical differences in all the variables of primary outcome, with respect to its comparators.

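### Adverse-event counts have no onset limit, and the Visit 1 symptom recall starts before the first study drop, so pre-dose events and reactions to examination drops can enter primary outcomes

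*Combined protocol and SAP*

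**What the plan says.** **Symptoms.** Burning, foreign body sensation and itching are primary tolerability outcomes (6.4.1.2). Under 6.4.3.8 the subject is "questioned directly about the presence in general (since the last visit) of the following symptoms". The question is not tied to use of the study product.

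**First dose.** Treatment is assigned at the baseline visit on day 0 and given with the "indication to start the treatment period the next day (day 1") (6.5.1, Assignment).

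**Examination drops.** For each of the two stains, "A drop of topical anesthetic will be instilled in the conjunctival cul-de-sac" or equivalent wording applies (6.4.3.3.1). Tonometry uses tetracaine with fluorescein (6.4.3.5), and the posterior segment examination uses mydriatics (6.4.3.6). The schedule places staining and tonometry at screening, baseline, Visit 1 and the final visit, and mydriasis at all of these except Visit 1. The baseline examinations may be taken over from screening at the investigator's choice (schedule footnote 1; 6.5.1.2). The elimination criteria foresee reactions to the test agents: "No tolerability or hypersensitivity to any of the compounds used during the tests (fluorescein, green lysine, tetracaine") (6.2.3).

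**Adverse events.** These are a primary safety outcome (6.4.1.1), collected at every contact from screening to the day 12 call (6.4.4 and schedule). For reporting, "all eyes of those participants who were randomly assigned to an intervention group after the baseline visit will be considered" (8.3.1). The date of occurrence and the investigator's view of the relationship to the product are recorded (9.3.1.1, 9.3.1.3).

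**Diary.** At Visit 1 the investigator reviews the diary to "evaluate postinstillation symptoms and record applications" (6.5.1.3). These entries appear in no outcome list and no analysis.

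**The concern.** A treatment-period outcome should start when treatment starts, and here two primary outcomes do not. The adverse-event rule says whose eyes are counted but not when an event must have begun. An event between screening and the first drop, in someone later randomised, can be counted under the product that person had not yet used. The symptom question at Visit 1 covers day 0, and at both post-baseline visits it can take in irritation from anesthetic and dyes.

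Two uses of the data are exposed. The specific objectives (5.5.2) describe each product on its own, and within-group tests are planned (8.3.1), so balance between arms does not protect those results. The between-group comparison feeds a rule in 8.3.1 that calls the product safe and tolerable when the primary outcomes show no difference from the comparator. A background shared by both arms shrinks a true difference and so makes that conclusion easier to reach.

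**Working it through.** The plan states no figure on this point, so there is none to reproduce. The check is a count of days, followed by an illustration with assumed rates.

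**1. Pre-dose share of the adverse-event window**

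Inputs: screening is X days before baseline, with X from 0 to 10 (6.4.4: no minimum, at most 10 days). First dose is on day 1. The call is on day 12 ± 1.

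Share = (X + 1) / (X + 1 + day of call)

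- X = 0, call on day 12: 1/13 = 8%
- X = 10, call on day 12: 11/23 = 48%
- Extremes over the call window: 1/14 = 7% (X = 0, day 13) to 11/22 = 50% (X = 10, day 11)

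With an onset limit at the first drop, the share is 0.

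**2. Pre-dose share of the Visit 1 symptom recall**

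Inputs: the recall starts on day 0, and Visit 1 is on day v = 3 ± 1 (6.4.4).

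Share = 1 / (v + 1): 1/3 = 33% for day 2, 1/4 = 25% for day 3, 1/5 = 20% for day 4.

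**3. Examination exposure inside each recall**

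- Visit 1 recall: if the examinations are done on day 0, anesthetic up to three times per eye (once per stain, once for tonometry), two dyes and mydriatics. If screening values are reused, none on day 0. The exposure therefore differs by subject.
- Final-visit recall: the anesthetic and dyes of Visit 1, in every subject examined then. No mydriasis is scheduled at Visit 1.

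**4. What a shared background would do (illustration only)**

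The documents give no rate of pre-dose events or examination reactions. Assume the same background probability b in both arms, independent of the product effect:

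p′ = 1 − (1 − p)(1 − b), so the difference between arms becomes (p₂ − p₁)(1 − b).

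Take p₁ = 7.3%, the adverse-event rate quoted in 6.6.1, and p₂ = 40%, an assumption, because 6.6.1 does not state the second proportion clearly. With n = 15 per group and two-sided alpha 0.05, power = Φ[(d − 1.96·SE₀)/SE₁]. Here d is the difference, SE₀ = √(2·p̄(1 − p̄)/n) with p̄ the mean of the two rates, and SE₁ = √([p₁′(1 − p₁′) + p₂′(1 − p₂′)]/n).

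| b | p₁′ | p₂′ | Difference | Expected cases in 15 at p₁′ | Power |
|---|---|---|---|---|---|
| 0 | 7.3% | 40.0% | 32.7 points | 1.1 | 56% |
| 5% | 11.9% | 43.0% | 31.1 points | 1.8 | 48% |
| 10% | 16.6% | 46.0% | 29.4 points | 2.5 | 41% |
| 20% | 25.8% | 52.0% | 26.2 points | 3.9 | 31% |

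The direction does not depend on these choices: for any b above zero the rates rise and the difference shrinks by the factor 1 − b. The amounts do depend on them.

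**The case against.** **Nothing is attributed to the products.** A reader might infer that the plan blames pre-dose events or examination reactions on the study products. It does not. Onset date and relationship are recorded, and the causality algorithm in 9.3.1.4 asks about timing and alternative causes. Pre-dose adverse events can therefore be separated from data already planned. This stands. What is missing is a sentence in 8.3.1 saying that they will be. Collecting adverse events from screening is not the fault. The symptom scores have no onset or causality item, so for them the gap cannot be closed afterwards.

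**The 8.3.1 sentence may already set a time limit.** It mentions the baseline visit, but the words qualify when participants were assigned. Even read as a limit on events, it would start on day 0, before the first drop.

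**The recall may start when the previous visit ended.** On that reading, reactions during the examination itself are excluded. The reading is possible, but the text does not settle it, and day 0 after the visit still precedes dosing.

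**The arms are balanced.** Both follow the same schedule under randomisation and masking, and symptoms are also asked at screening and baseline. This stands against any claim that one arm is favoured. It does not help the per-product description, nor does it prevent dilution.

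**The effect may be small.** Table 6 scores itching by frequency, which a brief reaction should barely move; burning and foreign body sensation are listed by severity. Subjects intolerant of a test agent are eliminated, which limits the influence of marked reactors on the final visit. The size is unknown and may be modest.

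**Conclusion.** The concern holds as a gap in outcome definition. Followed as written, the plan lets adverse events before the first drop be counted under a product, and lets symptoms from day 0 or from examination drops enter the primary tolerability scores. The exposed share of time is 8% to 48% for adverse events (day 12 call) and 20% to 33% for the Visit 1 recall. These are calendar days and cannot be read as shares of events. The table of power losses rests on an assumed background rate and an assumed 7.3% versus 40% contrast; it shows direction only.

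A reader might go further and infer a bias towards PRO-174 over the comparator, or results that cannot be interpreted. The documents support neither: the contamination is expected to be balanced. What remains is inflated rates for each product and some loss of contrast, under a decision rule that rewards finding no difference. The symptom half is the stronger because it cannot be repaired after collection. The change is worth making before data collection.

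**What to change.** **In 8.3.1:** tabulate by product only adverse events with onset at or after the first study drop, using the recorded onset date, and list earlier events in randomised participants separately.

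**In 6.4.3.8 and the CRF:**
- At Visit 1, ask about symptoms since the first study drop.
- At the final visit, keep the present recall back to Visit 1, and state that reactions during that visit's own examination are not to be counted.
- At every visit, ask about symptoms before any examination drop is instilled.

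**Two limits.** The final-visit recall should not start on the day after Visit 1. Study drops applied later on the Visit 1 day would then fall in neither window, and Visit 1 may be on day 2, when 8 applications are scheduled. Diary entries on post-instillation symptoms should be supportive data and not the main source, since the diary form is not in the documents and its symptom scoring cannot be checked.

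**Cost:** a few lines of protocol and CRF wording, an order of questioning at each visit, and one date filter in the adverse-event table. No visit, procedure or subject is added. Delayed reactions to the Visit 1 examination drops can still appear in the final-visit recall; this remains a limitation to be stated.
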